331 Rectal AS administration yields pharmacokinetic results similar to those obtained from oral 332 administration, with the exception of delayed AS Cmax and longer AS half-life. Compared to IV 333 administration, expectedly, both AS absorption and elimination are prolonged following rectal administration. Following rectal administration of AS, Tmax average between 0.58-1.43 hours. 334 with a half-life between 0.9-.95 hours.²⁹ These averages are based on three different studies: two 335 336 studies containing pediatric patients with uncomplicated falciparum malaria (10 - 20mg/Kg 337 dosing)^{40,41} and one study containing healthy Malaysian adults (200 mg rectal suppository, 338 ~4mg/Kg dosing). 42 Following rectal dosing of a one-time 200 mg AS suppository in healthy 339 adults (similar to our planned dosing), a Cmax, Tmax, half-life and AUC of 448.5 ng/ml, 1.43 340 hours, 0.95 hours, and 796 ng*hr/ml of AS were observed, and Cmax, Tmax, half-life and AUC 341 of 385.6 ng/ml, 1.80 hours, 1.21 hours, and 965 ng*hr/ml respectively of DHA were observed in 342 healthy adults. 42 No data are available on rectal PK in adults with malaria as this route of 343 administration is not used to treat malaria in adults. The longer half-life of AS following rectal 344 dosing (average 0.9-0.95 hrs) compared to IM (average 25.2 – 48.2 minutes), or IV (average less than 5 minutes) may reflect absorption rate-limited elimination of AS.²⁹ As is expected given 345 346 that rectal AS administration avoids by-pass metabolism, the discrepancy in AS and DHA AUC 347 values (796 ng*hr/ml and 965 ng*hr/ml, respectively), is not as striking with rectal, as compared with oral administration of AS (119 ng*hr/ml and 1331 ng*hr/ml, respectively). ²⁹ Similar to oral 348 349 administration, both DHA Tmax and half-life values were higher than that of AS following rectal 350 administration.29

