- 626 Dose: 200 mg daily for five consecutive days
- Route of administration: Intravaginal, using an intravaginal applicator
- Packaging and Labelling: Pessaries (vaginal inserts) for dispensing will be packaged in standard
- 629 prescription use plastic or cardboard containers. Proper labeling will be applied per state
- 630 regulations.
- 631 **Storage and Stability:** The inserts may be stored at controlled room temperature. Inserts for
- dispensing will be packaged in a plastic or cardboard container and kept in their plastic mold until
- 633 administration.

- Administration Instructions: All study participants will receive detailed counselling and
- instructions on artesunate use prior to administration, including instruction to wash their hands before and after inserting the pessaries. At the time of visit 1, after a negative pregnancy test is
- confirmed, the study physician or nurse will provide the first vaginal insert, applicator, and
- 639 tampon. During that visit, the subjects will be instructed on the vaginal application of Artesunate
- inserts using the applicator provided, followed by the study-provided tampon. Tampons should
- be kept in place after each artesunate insert for at least 4 hours, but no longer than 10 hours.
- Tampons should be discarded properly, away from children and pets. Once the tampon is
- removed, participants will be advised to thoroughly wash their hands, and wipe outside of their
- genital area (vulvar and perianal) to remove any residue of the drug. To minimize irritation,
- participants will be advised not to engage in sexual contact (genital, anal, or oral sex) for at least
- 4 hours after applying the vaginal inserts, on days 1-5. Participants will return to the study clinic
- daily for visits 2-5 for self-administration of inserts numbers 2-5 as well as for review of any
- 648 adverse events. Participants will be advised not to douche during the five days of intravaginal
- artesunate use, and not to use any intravaginal ointments, gels, or other types of pessaries. For
- any bacterial or yeast vaginal infections, participants should use oral medication, which will be
- prescribed by the study doctor.

PI: [name] Version 1.0

- Dose rationale: The dose for this study (200 mg) was chosen based on a combination of
- 653 published clinical and pharmacokinetic data regarding intra-rectal administration of artesunate

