- screening activities, participants will have a malaria antigen test to screen for subacute malaria
- infection. Those who test positive will be referred for treatment and considered screen failure.

747 748

749

750

751

752

753

754

755

756 757

758

Screening/enrollment visit activities:

- Confirm eligibility
- Obtain informed consent
- Assign unique participant ID number
- Study protocol counselling (introduce the study to the participant, explain all study activities and timing, length, expectations of the participant, demonstration of intravaginal *Artesunate* application using pelvic model, discussion of tampon use etc.)
- Perform limited physical and pelvic exam and colposcopy with digital imaging
- Collect locator information
- Urine pregnancy testing
- Review concomitant/prohibited medications
- Obtain basic demographic and clinical data

759 760 761

762

Visit 1: Visit 1 can occur on the same day or up to 14 days following the screening/enrollment visit. Visit 1 will be timed to be no less than 1 week before the participant's anticipated menstrual cycle, for menstruating participants.

763764765

766

767 768

769 770

771

773

774

Visit 1 activities:

- Confirm eligibility
- Update locator information (if necessary)
- Review artesunate self-administration instructions and study protocol
- Review concomitant/prohibited medications
- Draw blood (~2.5ml) before artesunate self-administration
 - Artesunate self-administration using applicator, followed by tampon
- Observation for 30 minutes
 - Provide transport reimbursement
 - Schedule Visits 2

775 776

Visit 2-4: Visits 2, 3 and 4 must occur sequentially (within 24 hours) of each other. Attempts will be made to start visits at approximately the same time each day.

777 778 779

780

781

784

Visit 2-4 activities:

- Update locator information (if necessary)
- Review and record adverse events using standardized questionnaire
- Perform pelvic exam as needed based on AEs described (pelvic exam for suspected grade II or worse AEs)
 - Review concomitant/prohibited medications

- Artesunate self-administration using applicator, followed by tampon insertion
- Observation for 30 minutes
 - Provide transport reimbursement
 - Schedule subsequent visit

789 790

785

786

787

788

Visit 5: Visit 5 will occur one day (~24 hours) after Visit 4. Attempts will be made to start visits at the same time each day.

791 792 793

794

795

796 797

798

799

800 801

Visit 5 activities:

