- Update locator information (if necessary)
- Review and record adverse events using a standardized questionnaire
- Perform pelvic exam as needed based on AEs described (pelvic exam for suspected grade II or worse AEs)
- Review concomitant/prohibited medications
- Draw blood (~2.5ml) before artesunate self-administration & insert peripheral cannula for subsequent blood draws
- Artesunate self-administration using an applicator, followed by tampon insertion
- Blood draws (~2.5ml each time) at 15, 30min, 1h, 2h, 4h, 6h, and 8h after artesunate self-administration.
 - Provide transport reimbursement
- 805 Schedule visit 6

806 Visit 6: Visit 6 will occur 4-10 days after visit 5

807 808

809

804

Visit 6 activities:

- Review and record adverse events since last visit using standardized questionnaire
- Perform pelvic exam and colposcopy with digital imaging
- 811 Study exit/termination
- 812 Provide reimbursement

813814

817 818

819

820

b. 4.3 Adverse Event Reporting

815 **Definitions** 816 An adverse

An adverse event (AE) is any untoward medical occurrence in a patient or clinical investigation participant administered a pharmaceutical product and which does not necessarily have a causal relationship with this treatment. An adverse event can therefore be any unfavorable and unintended sign (including an abnormal laboratory finding), symptom, or disease temporally associated with the use of a medicinal (investigational) product, whether or not related to the medicinal (investigational) product.

821 822 823

824

825

An unexpected (unlisted) adverse event is an adverse reaction, the nature or severity of which is not consistent with the applicable product information (e.g., Investigator's Brochure for an unapproved investigational product or package insert/summary of product characteristics for an approved product).

826 827 828

A serious adverse event (SAE) is any untoward medical occurrence that at any dose:

PI: [name] Version 1.0

- 829 results in death;
- 830 is life-threatening;
- * requires inpatient hospitalization or prolongation of existing hospitalization;
- results in a persistent or significant disability/incapacity; or
 - is a congenital anomaly/birth defect

833 834 835

Important medical events as assessed by medical and scientific judgment may also be considered SAEs by the investigator and should be reported in an expedited fashion.

836 837 838

839

840

841 842

843

844 845

846

847 848

849

850

851

852

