4.4 Specimen collection, processing, storage and analysis

For each participant, ~2.5 ml of blood will be collected at each timepoint at baseline (Day 1), and on day 5 prior to administration of intravaginal artesunate (time 0), and at 15, 30min, 1h, 3h, and 6h after administration. Blood will be collected in gold/yellow top tubes and centrifuged to plasma which will be stored at -80°C until analyzed. Samples will be stored at Kenya Medical Research Institute (KEMRI)-affiliated accredited laboratories in Kisumu, Kenya, with cold chain maintained from collection to storage until shipping for analysis. All study staff as well as laboratory staff will be trained on study SOPs.

DHA and artesunate plasma testing: Specimens will be tested at the Walter Reed Army Institute of Research, (WRAIR) Division of Experimental Therapeutics laboratory in Maryland, USA which has validated DHA and artesunate assays. Analysis will be led by [name], D.O Chief of Clinical at the Walter Reed Army Institute of Research and the Clinical Pharmacology Fellowship Program Director. Plasma samples will be shipped under cold chain and remain frozen at at -80°C in WRAIR laboratory facilities until ready for analysis. Analysis will be performed using a validated high-performance Liquid Chromatography Mass Spectrometry (LCMS) assay at WRAIR with limits of quantification of Artesunate and DHA of approximately 80nM and 70 nM, respectively. 31,71 Quality control (QC) samples will be included with each assay batch, with a requirement that the run is acceptable only if the QC is within +/-15% of the nominal value. 35 The WRAIR Division of Experimental Therapeutics, Drug Metabolism and Disposition has over 75 years' experience with drug and product development, having achieved U.S FDA approval of 9 malaria drugs and more than 65 investigational new drug applications. All appropriate material transfer agreements and shipping licenses will be obtained from all relevant regulatory bodies including the Amref ESRC before specimen shipping is done. All specimens will be destroyed following testing. Each sample will be assigned a unique code number, and no identifiable personal health information (PHI) will be on the specimen label.

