Pharmacokinetic analysis: Conventional pharmacokinetic parameters - AUC (0, infinity), half-life, apparent clearance, the volume of distribution, maximum plasma concentration (Cmax), time to Cmax will be determined from the plasma concentration-time data using noncompartmental analysis. Peak plasma concentration (Cmax) and time to reach peak concentration (tmax) for artesunate and DHA will be the observed values. The AUC of AS will be calculated by linear trapezoidal summation with extrapolation to infinity. With respect to

DHA, AUC will be calculated to the last drug measurable time point. The elimination rate constant (β), will be calculated from the slope of the terminal phase of the log concentration-time profile, and the elimination half-life (t1/2) calculated from the ratio of ln 2/ β . Other PK parameters will be calculated using standard model-independent formulae.³⁹ The estimates of PK parameters for DHA will assume complete conversion of AS to DHA as reported previously.³⁵ Data will be plotted graphically and analyzed using statistical software. Data will be presented as mean with standard deviation (SD).

Compliance Statement: Biospecimen collection for this study will be conducted in full accordance with all applicable University of North Carolina (UNC) Research Policies and Procedures including Good Clinical Practice (CGP) policies, and all applicable Federal and state laws and regulations including 45 CFR 46, and the Health Insurance Portability and Accountability Act Privacy Rule, as well as the in-country regulatory agencies including the Amref Ethics and Scientific Review Committee (ESRC), the Kenya Pharmacy and Poisons Board (PPB), the National Commission for Science, Technology & Innovation (NACOSTI) and any other regulatory bodies required in-country. Any episode of noncompliance will be documented. The investigators will perform the study in accordance with this protocol, will obtain consent, and will report unexpected problems in accordance with the UNC IRB Policies and Procedures and all federal requirements. Collection, recording, and reporting of data will be accurate and will ensure the privacy, health, and welfare of research participants during and after the study.

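### The primary DHA AUC stops at the last measurable draw (8 h or 6 h, depending on the section) although dosing is 24-hourly; if vaginal absorption is slow, exposure is under-recorded in the expected direction

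*Combined protocol and SAP*

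**What the plan says.** Section 4.4 (Pharmacokinetic analysis), repeated in 4.5.2, gives two rules. For artesunate: "The AUC of AS will be calculated by linear trapezoidal summation with extrapolation to infinity". For DHA, whose Day 5 AUC is the primary endpoint: "DHA, AUC will be calculated to the last drug measurable time point". The same paragraph opens with a list that is not limited to AS: "Conventional pharmacokinetic parameters - AUC (0, infinity), half-life, apparent clearance". No section names an interval for the DHA AUC.

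The sampling window is stated in two ways. Section 4.2, Visit 5, has "Blood draws (~2.5ml each time) at 15, 30min, 1h, 2h, 4h, 6h, and 8h after artesunate self-administration", and the synopsis, protocol summary, section 1.7 and study schema agree. The specimen paragraph of 4.4 has "and at 15, 30min, 1h, 3h, and 6h after administration". The lay summary counts six Day 5 draws, which fits the shorter list.

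On dosing interval: "Visit 5 will occur one day (~24 hours) after Visit 4". On the tampon, section 3.2 says it should "be kept in place after each artesunate insert for at least 4 hours, but no longer than 10 hours".

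Section 4.5.2 compares mean DHA AUC with historical IV, oral and rectal values by a one-sample t-test at 0.05. Section 1.6 says that no vaginal absorption data exist.

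**The concern.** On Day 5 of daily dosing the natural exposure measure is AUC over the 24 h dosing interval. A rule that stops at 8 h gives the same answer only if almost all the drug has come and gone by then. If DHA is still measurable at 8 h, the other 16 h count as zero.

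The short half-lives behind the sampling window come from other routes. For the rectal route, section 1.3 remarks that the longer AS half-life "may reflect absorption rate-limited elimination of AS". Sections 1.6 and 2.5 describe vaginal epithelium as thicker and less permeable than rectal. Slow absorption is therefore possible, although nothing in the documents shows it.

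The protocol expects low exposure, and the study is meant to confirm this in support of an argument about malaria resistance. Truncation can only lower the recorded AUC, so any error favours the expected result.

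**Working it through.** **Plan's own figure.** The plan gives no figure for the share of AUC captured by the last draw. The sample size of 12 rests on convention, so it offers no effect size or SD to reproduce.

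**Inputs from the documents.** Rectal DHA after 200 mg (section 1.3): Cmax 385.6 ng/ml, Tmax 1.80 h, half-life 1.21 h, AUC 965 ng*hr/ml. DHA assay limit (4.4): 70 nM. Five doses, 24 h apart.

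**Assumptions.** DHA molecular weight 284.35, so the limit is 70 x 284.35 / 1000 = 19.9 ng/ml. One-compartment kinetics with elimination half-life 1.21 h. First-order absorption with half-life 2-8 h, or constant release over 8 or 10 h. True Day 5 AUC(0-24) set to 965.

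**Coherence of the rectal figures.** 0.5 x 1.80 x 385.6 + 385.6 x 1.21/0.693 = 347 + 673 = 1020, against the stated 965 (6% apart). That is close enough to use.

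**Fast case.** With rectal kinetics the 8 h level is 385.6 x 2^(-(8 - 1.80)/1.21) = 11 ng/ml. The tail is 11 x 1.21/0.693 = 19, and 19/965 = 2%. In the model, absorption half-lives of 0.5 and 1 h both record 922, a loss of about 4%.

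**Slow cases.** Linear trapezoid to the last value at or above 19.9 ng/ml:

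| Assumed input | 8 h level (ng/ml) | Recorded AUC, 8 h schedule | % of 965 | % of 965, 6 h schedule |
|---|---|---|---|---|
| Absorption half-life 2 h | 44 | 815 | 84.5 | 70 |
| 3 h | 55 | 710 | 73.6 | 58 |
| 4 h | 58 | 630 | 65.2 | 50 |
| 6 h | 58 | 529 | 54.8 | 41 |
| 8 h | 55 | 474 | 49.1 | 36 |
| Constant release, 8 h | 119 | 748 | 77.5 | 52 |
| Constant release, 10 h | 95.5 | 598 | 62.0 | 42 |

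Every 8 h level is above 19.9, so this loss is separate from the assay limit.

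**Effect on the test.** Suppose true exposure equals rectal and 65% is captured. The noncentrality is sqrt(12) x (0.65 - 1)/(0.65 x CV), which is -3.73 at a CV of 50%. With n = 12 and a two-sided 0.05 test (sidedness is not stated), the chance of a significantly lower result is 1.00, 0.92 and 0.68 at assumed CVs of 30%, 50% and 70%.

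**Check of the repair.** Add C8/lambda x (1 - exp(-16 x lambda)), with lambda from the 4, 6 and 8 h samples. At an absorption half-life of 4 h, C8 = 58.4 and lambda = 0.128, so the addition is 398 and the total is 630 + 398 = 1027 after rounding, 1.06 times the truth.

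| Absorption half-life | Total bounded at 24 h | Ratio to 965 | % extrapolated | Total to infinity |
|---|---|---|---|---|
| 2 h | 982 | 1.02 | 17 | 985 |
| 4 h | 1027 | 1.06 | 39 | 1086 |
| 6 h | 1046 | 1.08 | 50 | 1242 |
| 8 h | 1051 | 1.09 | 55 | 1431 |

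Extrapolating to infinity overshoots by up to 1431/965 = 1.48. Bounding at the dosing interval keeps the error to 2-9%. For constant release over 8 or 10 h the 4-8 h slope is not negative (lambda = -0.024), so there is no estimate.

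**The case against.** **No passage supports slow vaginal absorption.** The rectal AS half-life described as possibly absorption-limited is only 0.9-0.95 h, and those kinetics lose about 2%. Section 2.5 expects rapid elimination after vaginal use. This stands, and it makes the point conditional.

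**The plan does not clearly exclude extrapolation for DHA.** The general list names AUC to infinity. This also stands: the definition is contradictory, and which rule governs must be settled.

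**The 10 h limit proves little.** A reader might infer that the product is absorbed for up to 10 h. It is the tampon that may stay that long, it may be removed from 4 h, and nothing ties absorption to its presence.

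**Slow absorption would show elsewhere.** Tmax and half-life are reported and profiles are plotted. At absorption half-lives of 4-8 h the sampled Tmax would be 4 h, against 1.80 h rectally. The apparent half-life would be 0.693/0.128 = 5.4 h up to 0.693/0.058 = 12 h, against 1.21 h. A careful reader would be warned, but the primary AUC and its test would stay uncorrected.

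**Extrapolation can mislead.** In part this stands. An upper bound drawn as a log-linear line from 8 h to the assay limit at 24 h reaches roughly 1.4 to 2 times the truth under 8-10 h constant release. Using it in the t-test would replace one bias with another. The Day 5 pre-dose sample does not help: it is predicted at 3.8-14.1 ng/ml for half-lives of 4-8 h, below the limit. With 10% assay noise (assumed), about a quarter of constant-release profiles would show a chance decline from 4 to 8 h: the slope SE is 0.10/sqrt(8) = 0.035 and 0.024/0.035 = 0.68 SE. What counts as a decline must therefore be fixed in advance.

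**Conclusion.** The point holds as a conditional weakness of the primary endpoint. The DHA AUC has no fixed interval, its stopping rule conflicts with the general list in the same paragraph, and the last draw is at 8 h or 6 h depending on the section. On the 8 h schedule the loss is about 2-4% with rectal-like kinetics, about 15-50% at assumed absorption half-lives of 2-8 h, and 23-38% for constant release over 8-10 h. The 6 h schedule loses more. All errors run towards low exposure.

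A reader might go further and conclude that the primary result will be substantially too low. The documents do not support that, because vaginal absorption could be fast and no data settle it. The absorption rates, the CVs, the molecular weight and the one-compartment form are assumptions. The documents also do not say which AUC definition each historical comparator used, so the mismatch with those values cannot be sized.

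**What to change.** In 4.4 and 4.5.2, before any samples are analysed:

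1. State one definition of the primary DHA AUC, resolving the conflict between the general list and the DHA sentence, and reconcile the draw times across all sections. The formula below presumes the 8 h schedule. The shorter list has no 4 h or 8 h sample and would not support it.
2. Where the last sample is quantifiable and the late samples decline by a criterion written in advance, calculate Day 5 AUC(0-24) as the observed AUC to 8 h plus C8/lambda x (1 - exp(-16 x lambda)). Report it beside AUC to the last measurable point, with the percentage extrapolated.
3. Where no decline is seen, report AUC to the last measurable point as a lower bound only and make no lower-than-historical claim from it. Do not enter an upper-bracket value into the t-test.
4. Compare with historical values that use a matching AUC definition where available, and say where none is.

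The cost is wording and analysis only if the 8 h schedule stands. The downside is reliance on extrapolation in slow absorbers: 17-55% of the total, and 2-9% too high in the model. The reported percentage discloses this. If absorption is fast, the change is close to inert. The fix does not recover exposure that lies below the assay limit.

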In prior studies investigating multiple daily artesunate IV use in healthy subjects, Artesunate drug concentrations did not demonstrate accumulation, consistent with known rapid elimination rates of artemisinin derivates. 62 Following IV injection, artesunate drug levels rapidly declined and was converted to dihydroartemisinin (DHA) with overall mean elimination half-lives ranging from 0.15 - 0.23 hr for artesunate and 1.23 - 1.63 hours for DHA.²⁹ The differences between Artesunate and its principal metabolite are due to a combination of differences in solubility and to rapid conversion of Artesunate to DHA.³⁰ Despite the prediction of low systemic concentration of the drug, rapid elimination following intravaginal administration would be expected, as seen with IM administration.³⁰ Similarly, a significantly lower maximum plasma concentration after intra-vaginal administration is expected, compared to IV

CONFIDENTIAL

PI: [name] UNIVERSITY OF NORTH CAROLINA Version 1.0 April 25, 2023

573 administration, or rectal administration given higher vascularity of rectal mucosa compared to 574 cervicovaginal mucosa. Unlike vaginal tissue which consists of a thick, stratified squamous epithelial cell layer, ⁵⁸ rectal mucosa has only a single-cell layer of columnar epithelium which is 575 6-8 fold thinner than the vaginal epithelial layer, making it more permeable to drugs. 66 576

577

578 Current precancer studies dose intravaginal artesunate for 5-days on Week 1, 3, and 5, or Week 579 1, 3, 5, 7, with Weeks 2, 4, 6, or Weeks 2, 4, 6, 8 drug-free, respectively. That is, each 5-day 580 cycle is followed by a one week (at least 7 days) of no drug use in between each cycle. Given the 581 short half-life of DHA following daily dosing of Artesunate in adults, we expect no

582 accumulation after each 5-day cycle when following a drug-free week. As such, this study will 583 measure blood serum levels of DHA and artesunate following only one 5-day cycle of daily 584 applications of 200 mg artesunate pessaries in studying PK of the artesunate pessaries following intravaginal use for this indication.

585

586 587

588

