- 1151 4. Time to maximum concentration (Tmax) of Artesunate following 5-day self-administration of
- 1152 200mg Artesunate vaginal inserts (pessaries)
- 1153 Endpoint: Mean Artesunate Tmax (mins) with standard deviation on Day 5
- 1154 Statistical analysis: Mean artesunate Tmax (mins) will be compared to historical studies after IV,
- 1155 oral, and rectal administration among adults following similar dosing. Results will be analyzed
- 1156 using the Mann-Whitney U-test for nonparametric data, and a p-value of 0.05 considered
- 1157 statistically significant.
- 1159 5. Time to maximum concentration (Tmax) of DHA following 5-day self-administration of
- 1160 200mg Artesunate vaginal inserts (pessaries)
- 1161 Endpoint: Mean DHA Tmax (mins) with standard deviation on Day 5
- Statistical analysis: Mean DHA Tmax (mins) will be compared to historical studies after IV, oral 1162
- 1163 and rectal administration among adults following similar dosing. Results will be analyzed using
- 1164 the Mann-Whitney U-test for nonparametric data and a p-value of 0.05 considered statistically
- 1165 significant. 1166

1150

1158

- 1167 6. Artesunate half-life (t_{1/2}) following 5-day self-administration of 200mg Artesunate vaginal
- 1168 inserts (pessaries)
- 1169 Endpoint: Mean Artesunate half-life $(t_{1/2})$ (mins) with standard deviation on Day 5
- 1170 Statistical analysis: Mean Artesunate half-life $(t_{1/2})$ (mins) will be compared to historical studies
- 1171 after IV, oral and rectal administration among adults following similar dosing. Results will be
- analyzed using the Mann-Whitney U-test for nonparametric data and a p-value of 0.05 1172
- 1173 considered statistically significant.
- 1175 7. DHA half-life $(t_{1/2})$ following 5-day self-administration of 200mg Artesunate vaginal inserts
- 1176 (pessaries)

1174

1182

- 1177 Endpoint: Mean DHA half-life (mins) with standard deviation on Day 5
- 1178 Statistical analysis: Mean DHA half-life (t_{1/2}) (mins) will be compared to historical studies after
- 1179 IV, oral and rectal administration among adults following similar dosing. Results will be
- 1180 analyzed using the Mann-Whitney U-test for nonparametric data and a p-value of 0.05
- 1181 considered statistically significant.
- 1183 8. Apparent clearance of Artesunate (AS) following 5-day self-administration of 200mg
- 1184 Artesunate vaginal inserts (pessaries)
- Endpoint: Mean Artesunate clearance (L/Kg/hr) with standard deviation on Day 5 1185

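### The terminal slope after vaginal dosing is labelled elimination and the artesunate half-life is tested against IV values, so slow absorption could be reported as slower elimination

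*Combined protocol and SAP*

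**What the plan says.** The pharmacokinetic analysis paragraph of section 4.4 (Specimen collection, processing, storage and analysis) says: "The elimination rate constant (β), will be calculated from the slope of the terminal phase of the log concentration-time profile". It then has "the elimination half-life (t1/2) calculated from the ratio of ln 2/ β". The same rule is repeated at the end of section 4.5.2 (Data Analysis Plans).

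Secondary outcomes 6 (artesunate) and 7 (DHA) in section 4.5.2 compare the resulting Day 5 half-lives with historical studies "after IV, oral and rectal administration among adults following similar dosing", using a Mann-Whitney test at 0.05. V/F is a separate secondary outcome for each analyte (10 and 11), obtained by model-independent formulae that are not written out.

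The rectal paragraph of section 1.3 makes two statements about artesunate. One is that "both AS absorption and elimination are prolonged following rectal administration". The other is that the longer rectal half-life, set against the IM and IV values, "may reflect absorption rate-limited elimination of AS". Neither analysis paragraph takes up the second statement. They contain no check for absorption-limited kinetics and no rule for reading a difference from IV. The limitations in section 4.7 do not mention it.

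**The concern.** After IV dosing the terminal slope reflects disposition alone. After dosing by another route it reflects whichever is slower, input or elimination. A pessary in a hydrogenated vegetable oil base, followed by a tampon kept in place for 4 to 10 hours (sections 3.1 and 3.2), could plausibly keep releasing drug through much of the 8-hour sampling window. If it does, the parameter called elimination half-life is an absorption half-life. A significant difference from IV would then show only that vaginal input is slow.

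The protocol's own background shows how easily this is misread, because section 1.3 describes rectal elimination as prolonged a few lines before offering absorption as the explanation. The pattern is also not confined to the rectal route. The other extravascular artesunate half-lives in section 1.3 (IM 25.2 to 48.2 min, oral 20 to 45 min) also exceed the IV figure of under 15 min. After IM dosing the section reports a larger artesunate volume, although bioavailability judged by DHA exposure is above 86%.

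At stake are a wrong statement about artesunate elimination by a route with no earlier data, and possibly an inflated distribution volume.

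**Working it through.** **Inputs from the documents**
- Artesunate, IV: half-life under 15 min, clearance 2–3 L/kg/h, volume 0.1–0.3 L/kg (section 1.3); half-lives of "0.15 - 0.23 hr for artesunate and 1.23 - 1.63 hours for DHA" (section 2.5); under 5 min (section 1.3, rectal paragraph).
- Artesunate, rectal: 0.9–0.95 h, with 0.95 h for 200 mg in healthy adults (section 1.3).
- DHA: rectal 1.21 h (section 1.3), IV 1.23–1.63 h (section 2.5).
- Day 5 samples at 0.25, 0.5, 1, 2, 4, 6 and 8 h (section 4.2, Visit 5).

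**Assumed, not in the documents:** first-order absorption into one compartment, with a vaginal absorption half-life between 0.05 and 4 h.

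**1. The plan's IV figure.** Half-life = ln 2 × V/CL.
- Lowest: 0.693 × 0.1/3 = 0.023 h = 1.4 min.
- Highest: 0.693 × 0.3/2 = 0.104 h = 6.2 min.

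This agrees with under 15 min, but not with section 2.5 (0.15–0.23 h = 9–13.8 min). The steps below use section 2.5.

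**2. Rectal to IV ratio, artesunate.** 0.95/0.23 = 4.1 and 0.95/0.15 = 6.3. With 0.9 h the range is 3.9 to 6.0. Against the 15-minute bound the ratio is at least 0.9/0.25 = 3.6.

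**3. What the slope measures.** C(t) ∝ ka/(ka − ke) × (exp(−ke·t) − exp(−ka·t)). When ka < ke the term exp(−ka·t) survives longest, so the terminal slope tends to ka. Elimination was held at the IV value and the slope fitted to the last three scheduled samples:

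| Absorption half-life (h) | Reported half-life, true 0.15 h | Reported half-life, true 0.23 h | Ratio to true value |
|---|---|---|---|
| 0.1 | 0.15 | 0.23 | 1.0 |
| 0.5 | 0.50 | 0.50 | 3.3 and 2.2 |
| 0.95 | 0.95 | 0.95 | 6.3 and 4.1 |
| 2 | 2.00 | 2.00 | 13.3 and 8.7 |

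**4. V/F.** If V/F = (CL/F)/β, the reported value over the true value is β(true)/β(reported), which equals the half-life ratio. That is 4.1 to 6.3 for a rectal-like profile, whatever the bioavailability.

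**5. DHA.** Rectal over IV is 1.21/1.63 = 0.74 to 1.21/1.23 = 0.98, so there is no sign of absorption limitation. A chain from absorption through artesunate (half-life 0.2 h) to DHA, with true DHA half-life 1.23 and 1.63 h, gives:
- absorption 0.5 h: 1.26 and 1.66 h;
- absorption 0.95 h: 1.54 and 1.97 h;
- absorption 2 h: 2.78 and 3.48 h.

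The 0.95 h row exceeds the observed rectal 1.21 h. The figures come from different studies, so the chain is illustrative and not a fit to the rectal data.

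**6. What the IV test would detect.** In 1,000 simulated trials per setting, the two-sided Mann-Whitney test was significant for artesunate in 3.5% and 4.8% (true half-life 0.15 and 0.23 h) with absorption at 0.05 h. It was significant in 100% at 0.5 h or more, with elimination unchanged throughout. Assumed: 12 participants, 12 individual historical IV subjects, 30% between-subject CV, 10% assay error, no values below the quantification limit.

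**The case against.** The strongest reply is that this is a caveat on a label. Half-life and V/F are secondary, IV is one of three comparators, and the section 1.3 remark concerns rectal artesunate only. It is not a statement about every non-IV slope, about DHA or about the vaginal route. Sections 1.6 and 2.5 argue for lower vaginal permeability and lower concentrations, but give no absorption rate. All of that stands, and it makes the point conditional.

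Estimability is a further limit. The artesunate quantification limit of about 80 nM is 80 × 384.4/1000 = 30.8 ng/ml. Oral 200 mg gave a Cmax of 58 to 67 ng/ml (section 1.3), only log2(58/30.8) = 0.9 to log2(67/30.8) = 1.1 half-lives above it. Section 5.4 expects little or no systemic drug. So the slope may often not be estimable, and a reader should not infer that the trial will report a longer half-life, only that it can. The 100% in step 6 leaves this out.

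Three other stronger readings are tempting and fail:
- **A longer half-life would undermine the no-accumulation case for one cycle.** It would not. At a 3 h half-life the 24 h accumulation ratio is 1/(1 − 2^−8) = 1.004, whichever process sets the slope, and the Day 5 pre-dose sample checks carry-over directly.
- **DHA is affected in the same way.** The documents' rectal and IV figures show no effect.
- **The primary endpoint is affected.** DHA AUC to the last measurable time does not use β.

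It is also fair that the (CL/F)/β formula is assumed, and that oral and rectal slopes may share the problem.

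What the reply does not remove is the test itself. An IV comparison of this half-life cannot separate slow input from slow elimination, and the plan labels the result elimination.

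**Conclusion.** The concern holds for artesunate half-life, on two conditions: artesunate is quantifiable in enough late samples, and vaginal absorption is slower than elimination. The reported elimination half-life is then an absorption half-life. It would be 4.1 to 6.3 times the IV value for a rectal-like profile, with V/F inflated equally under the usual formula.

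For DHA the effect appears only with an absorption half-life of roughly 1 h or more, which the documents neither state nor exclude.

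A reader might go further and treat any half-life longer than IV as proof of absorption-limited input. The documents do not support that either, because a single-arm study without IV dosing can neither confirm nor exclude it. The defensible rule only bars the elimination reading.

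**What to change.** In secondary objectives 6 and 7, secondary outcomes 6 and 7, and both pharmacokinetic analysis paragraphs (sections 4.4 and 4.5.2):
- Rename β and t½ as apparent terminal rate constant and apparent terminal half-life.
- Delete the IV significance test for artesunate half-life and show the IV value descriptively. For DHA, keep any IV comparison descriptive, with the same caveat.
- State that a terminal half-life longer than IV is not evidence of slower elimination, and may reflect absorption-limited input that this study cannot confirm or exclude.
- Report V/F descriptively with that caveat, and write out its formula.

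Two reconciliations belong with this edit. The IV artesunate half-life is given as under 15 min, under 5 min and 9–13.8 min, so the reference shown must be named. The Day 5 sampling times also differ between section 4.2 (to 8 h) and section 4.4 (15 and 30 min, 1, 3 and 6 h).

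The cost is wording and the loss of IV half-life testing that cannot by itself support a conclusion about elimination. No samples or participants are added.
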